11.3 Interim Analysis

The DSMB will conduct a single interim analysis for efficacy and safety at the anticipated halfway point of the trial, after enrollment of 650 patients. The pre-specified stopping boundary for efficacy will be a P value < 0.001 for the difference between group in the primary outcome using a Chi-square test. This conservative Haybittle–Peto boundary will allow the final analysis to be performed using an unchanged level of significance (two-sided P value < 0.05).

Finally, after the interim analysis, the DSMB will evaluate the rate of the primary outcome in the facemask group. If the incidence of the primary outcome in the facemask group differs from the original estimate, the DSMB may suggest an increase sample size that would maintain the pre-planned statistical power to detect the pre-planned relative risk difference in the primary outcome between groups.

11.4 Correction for Multiple Testing

We will analyze a single pre-specified primary outcome and a single pre-specified secondary outcome. Consistent with recommendations of the Food and Drug Administration⁶⁰ and the European Medicines Association,⁶¹ each will be tested using a two-sided P value with a significance level of 0.05. For all other analyses except safety analyses, emphasis will be placed on the estimate of effect size with 95% confidence intervals, as recommended by the *International Committee of Medical Journal Editors*,⁶² and no corrections for multiple comparisons will be performed.

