8. RECORDED STUDY OUTCOMES

8.1 Primary Outcomes

- Hypoxemia, defined as a peripheral oxygen saturation < 85% during the interval between induction and 2 minutes after tracheal intubation

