8.2 Secondary Outcomes

- Lowest oxygen saturation during the interval between induction and 2 minutes after tracheal intubation

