settings, detecting a 6% absolute decrease in the incidence of hypoxemia with 85% power at a two-sided alpha level of 0.05 would require enrollment of 1,264 patients (632 per group). Anticipating missing data for up to 3% of patients, we will plan to enroll a total of 1,300 patients (650 per group). This sample size calculation was performed in PS version 3.1.2.

11.2 Statistical Analysis:

Prior to the conclusion of enrollment, we will make publicly available a complete, final statistical analysis plan. Analyses conducted in accordance with the statistical analysis plan will be identified as *a priori*. Any additional analyses requested by the investigators or reviewers will be identified as *post hoc*.

11.2.1 Primary Analysis:

The primary analysis will be an unadjusted, intention-to-treat comparison of patients randomized to preoxygenation with non-invasive positive pressure ventilation versus patients randomized to preoxygenation with facemask oxygen with regard to the primary outcome. The difference between the two study groups will be compared using a Chi-squared test.

11.2.2 Secondary Analysis:

We will perform intention-to-treat comparisons of secondary, exploratory, and safety outcomes. Continuous outcomes will be compared with Wilcoxon Rank Sum test and categorical variables with the Chi-squared test. Data on patient characteristics will be summarized as number and proportion for categorical variables and as median and interquartile range for continuous variables.

We will also perform an adjusted comparison of the primary outcome between groups using a generalized linear mixed effects model including a random effect for site and fixed effects for group assignment and the following pre-specified baseline variables:

1. Age;
2. Sex;
3. Race and Ethnicity;
4. BMI;
5. Location at enrollment (ED or ICU)
6. Highest fraction of inspired oxygen in the hour prior to initiation of preoxygenation;
7. APACHEII score; and
8. Indication for intubation (hypoxic respiratory failure: Yes vs No)
9. Operator experience (number of previous intubations the operator has performed)

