Exploratory clinical	28-d in-hospital mortality.
	Ventilator-free days to 28 d.
	ICU-free days to 28 d.

Sample Size Estimation

The current trial is designed to detect a 6% absolute difference between groups in the incidence of hypoxemia, a difference that is similar to or smaller than the difference considered to be clinically meaningful in the design of prior trials of oxygenation strategies during tracheal intubation.^{2,15} Assuming an incidence of hypoxemia of 17% in the oxygen mask group based on data from two recently completed trials by this network in similar ED and ICU settings, detecting a 6% absolute decrease in the incidence of hypoxemia with 85% power at a two-sided α level of .05 would require enrollment of 1,264 patients (632 per group).^{16,17} Anticipating missing data for up to 3% of patients, we plan to enroll a maximum of 1,300 total patients (650 per group). This

sample size calculation was performed in PS version 3.1.2 software (Vanderbilt University Medical Center).

Data and Safety Monitoring Board and Interim Analysis

The data and safety monitoring board and interim analysis are described in [e-Appendix 1](#).

Statistical Analysis Principles

Analyses will be conducted following reproducible research principles using R software (R Foundation for Statistical Computing). Categorical variables will be presented as number and percentage and will be compared between groups using a χ^2 test. Continuous variables will be presented as mean \pm SD or median

(interquartile range) and will be compared between groups using a Wilcoxon rank-sum test. We will present absolute between-group differences with associated 95% CIs. A two-sided P value of $< .05$ will define a statistically significant between-group difference in the primary outcome. With a single primary outcome, no adjustment for multiplicity will be made. For secondary, safety, and exploratory analyses, emphasis will be placed on the magnitude of differences between groups with 95% CIs, rather than statistical significance.

Main Analysis of the Primary Outcome

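### Protocol 11.4 gives the secondary outcome its own 0.05 test with no order, while the SAP sets a significance threshold for the primary only

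*Combined protocol and SAP*

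**What the plan says.** **Protocol v1.1, section 11.4.** The section opens with "We will analyze a single pre-specified primary outcome and a single pre-specified secondary outcome" and continues that "each will be tested using a two-sided P value with a significance level of 0.05". Only the remaining analyses, safety analyses excepted, are then moved to estimation with confidence intervals, and for those "no corrections for multiple comparisons will be performed". So 11.4 keeps the secondary outcome on the testing side. Neither this section nor any other gives a testing order, a gatekeeping rule or an alpha split.

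**Published SAP, Statistical Analysis Principles.** A two-sided P below 0.05 defines significance for the primary outcome. The stated reason for making no multiplicity adjustment is that there is only one primary outcome. The text then says: "For secondary, safety, and exploratory analyses, emphasis will be placed on the magnitude of differences between groups with 95% CIs, rather than statistical significance". The manuscript version of the SAP carries the same rule under the same heading.

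**The two outcomes.** Protocol 8.1: "Hypoxemia, defined as a peripheral oxygen saturation < 85% during the interval between induction and 2 minutes after tracheal intubation". Protocol 8.2: "Lowest oxygen saturation during the interval between induction and 2 minutes after tracheal intubation". The primary is the secondary cut at 85%. Under protocol 11.2.1 the primary is compared by a chi-squared test. For the other outcomes, 11.2.2 says "Continuous outcomes will be compared with Wilcoxon Rank Sum test and categorical variables with the Chi-squared test", which gives the secondary a rank-sum test.

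**The concern.** The SAP's reason for making no adjustment is that one outcome carries the inference. Section 11.4 sets up two, each at the full 0.05. The result for which the two rules diverge is easy to describe: hypoxemia gives P above 0.05 and lowest saturation gives P below 0.05. Under 11.4 the second finding may be called statistically significant. Under the SAP it is an estimate with an interval.

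This is not a matter of an old version set against a new one. The version log says that v1.1 (7 July 2023) was issued to bring the protocol into line with the SAP. It changed outcomes, covariates and subgroups, but section 11.4 reads the same in v1.0 and v1.1. At stake is how the secondary result may be worded in the report, and what overall error rate goes with that wording.

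**Working it through.** **1. The plan's own figure.** The documents state no error rate across the two outcomes. The nearest figure is the sample size, which shows where the 0.05 was spent. Inputs from protocol 11.1: 17% versus 11%, 85% power, two-sided 0.05.

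- Uncorrected: n = [1.960·√(2·0.14·0.86) + 1.036·√(0.17·0.83 + 0.11·0.89)]² / 0.06² = 599.0, or 600 per group after rounding up.
- With continuity correction: (n/4)·[1 + √(1 + 4/(n·0.06))]² = 631.9, or 632 per group and 1,264 in total. This matches the plan.

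The design was sized on the primary alone, at the full 0.05.

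**2. Bounds for two tests at 0.05 each.** The upper bound is 0.05 + 0.05 = 10%. If the tests were independent: 1 − 0.95² = 9.75%.

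**3. Correlation under no effect.** The documents give none, but it follows from the definitions. Let p be the overall share of patients below 85%, I the indicator of being in that lowest share, and U the rank scaled to 0–1. Then:

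- Cov(I, U) = p²/2 − p/2 = −p(1 − p)/2
- SD(I) = √(p(1 − p)) and SD(U) = 1/√12
- |correlation| = √(3p(1 − p))

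The chi-squared and rank-sum statistics share this correlation under the null. The value of p is an assumption, taken over 10% to 20% to bracket the planned 17%.

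**4. Chance that at least one P is below 0.05.** This is 1 − Pr(|Z₁| < 1.96 and |Z₂| < 1.96), from a bivariate normal with that correlation.

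| Assumed p | Correlation | At least one false positive | Excess over 5% |
|---|---|---|---|
| 10% | 0.52 | 9.0% | 4.0 points |
| 14% | 0.60 | 8.8% | 3.8 points |
| 17% | 0.65 | 8.6% | 3.6 points |
| 20% | 0.69 | 8.4% | 3.4 points |

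The excess consists entirely of trials in which the secondary alone is rejected.

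**5. Robustness.** At p of 11% to 17%, letting 10% to 40% of patients tie at 100% saturation changes the results by less than 0.1 point. A simulation with integer saturations, 630 per group and 20,000 runs gave 8.6% at p = 17% and 8.5% at p = 14%. Adding the interim look on the primary (P < 0.001 at half the information) gives 8.6% at 17% and 8.8% at 14%.

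**6. The primary alone.** Its error is 5.0% at the final analysis and 5.02% with the interim look. This is also the overall figure under no effect if the secondary carries no significance claim, or is tested only after a significant primary.

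**The case against.** The strongest reply is that the trial's conclusion rests on one primary outcome and one test. The sample size and the interim boundary use only that outcome, and its error is intact. Protocol 11.2 also defers to a complete final SAP and treats analyses done under it as the a priori ones. The published SAP (1 September 2023) is later than protocol v1.1, and under its rule the two-claim situation does not arise. All of this stands, and it makes the point modest. It does not remove the conflict: 11.4 is current protocol text, it gives the secondary its own threshold in plain terms, and nothing in it says that the SAP overrides it.

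Four stronger readings are tempting, and the documents do not support them.

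- *The trial has a 9% type I error.* It does not. The 8.4% to 9.0% applies only if neither outcome differs and the secondary is counted as a claim in its own right.
- *The trial could be declared successful on lowest saturation alone.* No section says that a secondary result establishes efficacy. What 11.4 permits is a stand-alone statement of significance.
- *The SAP rules out testing the secondary.* Its wording concerns emphasis, and it still plans a rank-sum comparison. The two documents differ on the status of the resulting P value, not on whether it is computed.
- *A primary miss with a secondary hit is likely because the continuous measure has more power.* Power concerns true effects and adds nothing to a false-positive rate. Its size also depends on a saturation distribution that the documents do not give. For 17% versus 11% with 632 per group, an assumed uniform normal shift gives the rank-sum test about 99.7% power. If instead 6% of patients move only from below 85% into the 85–90% band (assumed to hold 15% of mask patients and counted as ties), power is about 9%.

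**Conclusion.** The inconsistency is real and should be corrected. It is a conflict over the inferential status of the secondary outcome and does not affect the primary analysis. Its size is 3.4 to 4.0 percentage points above 5% under no effect, or 3.6 points at the planned 17%. That rests on an assumed overall hypoxemia rate of 10% to 20%, both null hypotheses being true, and the secondary being treated as a claim of its own. Nothing here calls into question the primary test, its alpha or the sample size.

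**What to change.** The least change is to amend protocol 11.4 to match the SAP. The two-sided 0.05 threshold would apply to the primary outcome only, and lowest oxygen saturation would be reported as a between-group difference with a 95% confidence interval and no stand-alone significance claim.

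If a significance claim on the secondary is wanted, an acceptable alternative is a fixed sequence stated in both documents: test the secondary at two-sided 0.05 only if the primary is significant at 0.05, and otherwise report the estimate and interval. This adds a conditional test that the SAP does not now contain, so it goes further than reconciliation.

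The first option costs one sentence in the protocol, the second one sentence in each document. Neither alters the primary test, its alpha or the 1,300 patients. The downside of both is that no significance claim on the secondary can be made when the primary misses; under the first option none is made in any case. Splitting alpha at 0.025 each would also hold the overall error (about 4.4% to 4.5%), but at 632 per group it would lower the primary's power from 86.8% to 79.8% (uncorrected chi-squared), so it is the costlier route.

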11.5 Handling of Missing Data

No patients will be lost to follow up before the measurement of the primary outcome, but oxygen saturation may be unavailable in some cases (equipment malfunction, observer error during a rapid, emergency procedure, or cardiac arrest). Missing data will not be imputed for the primary outcome, or any of the secondary or exploratory outcomes. In adjusted analyses, missing data for baseline covariates will be imputed using multiple imputations.

12. Privacy and Confidentiality

All patients will be assigned a unique study ID number for use in the coded study database. Study personnel will access patients' electronic health records at three planned time points: immediately following enrollment; when collecting baseline demographics and comorbidities (may occur anytime between enrollment and final data collection); and when collecting clinical

outcomes (any time after the first of discharge or 28 days following intubation). The electronic health record may be accessed again, as needed, between enrollment and study publication to respond to queries from the coordinating center focused on ensuring data completeness and quality. The minimal PHI that is collected will be visible only to site investigators at the site where the patient was enrolled. The dataset for analysis will contain the unique study ID and no other patient identifiers. At the time of publication, a fully de-identified version of the database will be generated.

At no time during the course of this study, its analysis, or its publication will patient identities be revealed in any manner. The minimum necessary data containing patient or provider identities will be collected. Data collected from the medical record will be entered into the secure online database REDCap. Hard copies of the data collection sheet completed at the time of the airway management event will be stored in a locked room until after the completion of enrollment and data cleaning. Following publication of the study results, all hard copies of data collection forms will be destroyed and the REDCap database will be fully de-identified in accordance with institutional regulations.

13. Follow-up and Record Retention

Patients will be followed after enrollment up to 28 days or until hospital discharge, whichever occurs first. Data collected from the medical record will be entered into the secure online database REDCap. Hard copies of the data collection sheet completed at the time of the airway management event will be stored in a locked room until after the completion of enrollment and data cleaning. Once data are verified and the database is locked, all hard copies of data collection forms will be destroyed. All data will be maintained in the secure online database REDCap until the time of study publication. The minimal PHI that is collected will be available only to site investigators at the site where the patient was enrolled. At the time of publication, a fully de-identified version of the database will be generated.

14. Safety Monitoring and Adverse Events

Assuring patient safety is an essential component of this protocol. Preoxygenation with non-invasive positive pressure ventilation and preoxygenation with facemask oxygen are both standard-of-care interventions that have been used in clinical practice for decades with an established safety profile. However, any trial conducted during a high-risk, time-sensitive procedure like tracheal intubation of critically ill patients raises unique safety considerations. This protocol addresses these considerations through:

1. Exclusion criteria designed to prevent enrollment of patients likely to experience adverse events from preoxygenation with non-invasive positive pressure ventilation or preoxygenation with facemask oxygen;
2. Systematic collection of outcomes relevant to the safety of preoxygenation with non-invasive positive pressure ventilation and preoxygenation with facemask oxygen;
3. Structured monitoring, assessment, recording, and reporting of adverse events.

14.1 Adverse Event Definitions

Adverse Event – An adverse event will be defined as any untoward or unfavorable medical occurrence in a human subject temporally associated with the subject’s participation in the research, whether or not considered related to the subject’s participation in the research. Any adverse event occurring during the research will be classified according to the following characteristics:

- **Seriousness** – An adverse event will be considered “serious” if it:
 - Results in death;
 - Is life-threatening (defined as placing the patient at immediate risk of death);
 - Results in inpatient hospitalization or prolongation of existing hospitalization;
 - Results in a persistent or significant disability or incapacity;
 - Results in a congenital anomaly or birth defect; or
 - Based upon appropriate medical judgment, may jeopardize the patient’s health and may require medical or surgical intervention to prevent one of the other outcomes listed in this definition.
- **Unexpectedness** – An adverse event will be considered “unexpected” if the nature, severity, or frequency is neither consistent with:
 - The known or foreseeable risk of adverse events associated with the procedures involved in the research that are described in the protocol-related documents, such as the IRB-approved research protocol; nor
 - The expected natural progression of any underlying disease, disorder, or condition of the subject experiencing the adverse event and the subject’s predisposing risk factor profile for the adverse event.
- **Relatedness** – The strength of the relationship of an adverse event to a study intervention or study procedure will be defined as follows:
 - Definitely Related: The adverse event follows (1) a reasonable, temporal sequence from a study procedure AND (2) cannot be explained by the known characteristics of the patient’s clinical state or other therapies AND (3) evaluation of the patient’s clinical state indicates to the investigator that the experience is definitely related to study procedures.
 - Probably or Possibly Related: The adverse event meets some but not all of the above criteria for “Definitely Related”.
 - Probably Not Related: The adverse event occurred while the patient was on the study but can reasonably be explained by the known characteristics of the patient’s clinical state or other therapies.
 - Definitely Not Related: The adverse event is definitely produced by the patient’s clinical state or by other modes of therapy administered to the patient.
 - Uncertain Relationship: The adverse event does not fit in any of the above categories.

14.2 Monitoring for Adverse Events

The time interval during which patients will be monitored for the occurrence of adverse events

begins at randomization and ends at the first of hospital discharge or 28 days. Adverse events occurring before randomization or after hospital discharge or 28 days will not be collected. The lead investigator at each enrolling site will have primary responsibility overseeing the monitoring, assessment, and reporting of adverse events. Site study personnel will evaluate for the occurrence of adverse events by manual review of the electronic health record and by communication with treating clinicians. Site study personnel will evaluate for the occurrence of adverse events by manual review of the electronic health record at two time points. The first will occur approximately 24 hours after randomization at the time of initial data collection. The second will occur at the first of hospital discharge or 28 days after enrollment at the time of final data collection. Study personnel at each site will also communicate regularly with the treating clinicians who perform tracheal intubation in the study environments between enrollment and 28 days after enrollment to solicit information about any potential adverse events. If study personnel at a site identify a potential adverse event, the lead investigator at the site will be immediately notified. The lead investigator at the site will assess the seriousness, unexpectedness, and relatedness of the potential adverse event. With assistance as needed from the coordinating center and the trial primary investigator, the lead investigator at the site will determine whether the event qualifies for recording and reporting.

14.3 Recording and Reporting Adverse Events

The following types of adverse events will be recorded and reported:

- Adverse events that are Serious and Definitely Related, Probably or Possibly Related, or of Uncertain Relationship.
- Adverse events that are Unexpected and Definitely Related, Probably or Possibly Related, or of Uncertain Relationship.

Adverse events that do not meet the above criteria will not be recorded or reported. Adverse events that the lead investigator at a site assesses to meet the above criteria for recording and reporting will be entered into the adverse event electronic case report form in the trial database. The lead investigator at the site will record an assessment of each characteristic for the adverse event, including seriousness, unexpectedness, and relatedness. For any adverse event that is **serious AND unexpected**, and definitely related, probably or possibly related, or of uncertain relationship, the lead investigator at the site will report the adverse event to the coordinating center and the trial primary investigator **within 24 hours** of becoming aware of the adverse event. For any other adverse event requiring recording and reporting, the lead investigator at the study site will report the adverse event to the coordinating center and the trial principal investigator **within 72 hours** of becoming aware of the adverse event. The coordinating center and the trial principal investigator will coordinate with the lead investigator at the site to obtain information about the adverse event regarding each characteristic for the adverse event, including seriousness, expectedness, and relatedness. The lead investigator at the site will be responsible for making final determinations regarding seriousness and unexpectedness. The coordinating center and trial principal investigator will be responsible for making final determinations regarding relatedness.

For adverse events that meet the above criteria for recording and reporting, the coordinating center will notify the DSMB, the IRB, and the sponsor in accordance with the following reporting plan:

Characteristics of the Adverse Event	Reporting Period
Fatal or life-threatening (and therefore serious), unexpected, and definitely related, probably or possibly related, or of uncertain relationship.	Report to the DSMB, IRB, and sponsor within 7 days after notification of the event.
Serious but non-fatal and non-life-threatening, unexpected, and definitely related, probably or possibly related, or of uncertain relationship.	Report to DSMB, IRB, and sponsor within 15 days of notification of the event.
All other adverse events meeting criteria for recording and reporting.	Report to DSMB in regularly scheduled DSMB safety reports.

The coordinating center will distribute the written summary of the DSMB's periodic review of reported adverse events to the IRB in accordance with NIH guidelines: (<http://grants.nih.gov/grants/guide/notice-files/not99-107.html>).

